7.1.2.2. Systemic Event Symptoms and Fever

7.1.2.2.1. Systemic Event Symptoms

For the first 7 days following Doses 1 to 4 and the Supplemental Dose, the subject's legally acceptable representative will be asked to assess decreased appetite, drowsiness/increased sleep, and irritability and to record the symptoms in the e-diary in the evening. The symptoms will be assessed by the subject's legally acceptable representative as mild, moderate, or severe according to the grading scale in Table 3 below. The subject's legally acceptable representative will also be instructed to contact site staff if the subject experiences any possible Grade 4 prompted systemic event (ie, emergency room visit or hospitalization for severe decreased appetite, severe drowsiness/increased sleep, or severe irritability) within 7 days after vaccination. Study staff may also contact the subject's legally acceptable representative to obtain additional information on Grade 3 events entered into the e-diary.

Only an investigator is able to classify a subject's systemic event as Grade 4, after physical examination of the subject or documentation from another medically qualified source (eg, emergency room or hospital record) or telephone contact with the subject's legally acceptable representative. If a subject experiences a Grade 4 systemic event, the investigator must immediately notify the sponsor.

The procedure for notification of the sponsor is provided in the SRM or equivalent.

Table 3. Grading Scales for Systemic Events

Systemic Event	Mild	Moderate	Severe	
	Grade 1	Grade 2	Grade 3	Grade 4 ^a
Decreased appetite	Decreased interest in	Decreased oral	Refusal to feed	Emergency room
(loss of appetite)	eating	intake		visit or
				hospitalization for
				severe decreased
				appetite (loss of
				appetite)
Drowsiness	Increased or	Slightly subdued,	Disabling, not	Emergency room
(increased sleep)	prolonged sleeping	interfering with daily	interested in usual	visit or
	bouts	activity	daily activity	hospitalization for
				severe drowsiness
				(increased sleep)
Irritability	Easily consolable	Requiring increased	Inconsolable; crying	Emergency room
(fussiness)		attention	cannot be comforted	visit or
				hospitalization for
(synonymous with				severe irritability
restless sleep;				(fussiness)
decreased sleep)				

Abbreviations: CRF = case report form; e-diary = electronic diary.

7.1.2.2.2. Fever

In order to record information on fever, a digital thermometer will be given to the subject's legally acceptable representative with instructions on how to measure rectal temperature at home. Temperature will be collected in the evening daily for 7 days following Doses 1 to 4 and the Supplemental Dose (Days 1 to 7, where Day 1 is the day of vaccination) and at any time during the 7 days that fever is suspected. Fever is defined as a rectal temperature of $\geq 100.4^{\circ} F$ ($\geq 38.0^{\circ} C$). The highest temperature for each day will be recorded in the e-diary. In the event of a fever on Day 7, temperature will be collected daily until fever has resolved (1 day of temperature less than $100.4^{\circ} F$ [$38.0^{\circ} C$]) in order to collect a stop date in the CRF. A subject's legally acceptable representative will be prompted to contact the investigator if the subject experiences a fever $\geq 104.0^{\circ} F$ ($\geq 40.0^{\circ} C$) to assess the fever and perform an unscheduled assessment. Study staff may also contact the subject's legally acceptable representative to obtain additional information if a temperature of $\geq 102^{\circ} F$ is entered into an e-diary. Temperature will be measured and recorded to 1 decimal place and then grouped into ranges for the analysis; see Table 4 below.

a. Grade 4 assessment should be made by the investigator; Grade 4 will not be collected in the e-diary but will be collected as an AE on the CRF. The severity of the systemic event should be graded using the AE severity grading scale in Section 8.3.

Table 4. Ranges for Fever

100.4°F to 101.1°F (38.0°C to 38.4°C)
101.2°F to 102.0°F (38.5°C to 38.9°C)
102.1°F to 104.0°F (39.0°C to 40.0°C)
>104.0°F (>40.0°C)

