6.1. Group 1 (Coadministration) Study Procedures

6.1.1. Group 1 Visit 1 (Dose 1: 2-Month Visit, Day 1)

Prior to randomization:

- A personally signed and dated informed consent document indicating that the subject's legally acceptable representative has been informed of all pertinent aspects of the study before performing any study-specific procedures.
- Record the subject's demographic information (including date of birth, sex, race, and ethnicity).
- Obtain and record the subject's medical history including prior vaccinations.
- Perform physical examination evaluating any clinically significant abnormalities within the following body systems: general appearance; skin; head, eyes, ears, nose, and throat; heart; lungs; abdomen; musculoskeletal; extremities; neurological; and lymph nodes. Clinically significant abnormal results will be recorded in the CRF.
- Measure and record the subject's rectal temperature (°F/°C).
- Ensure that all inclusion criteria, none of the exclusion criteria, and none of the temporary delay criteria are met.
- Assign randomization number and investigational product container numbers via the IRT.
 This must be the last step before proceeding. A site staff member will prepare the investigational product according to the IP manual.

After randomization:

- Administer a single 0.5-mL injection of c7vPnC into the left anterolateral thigh and a single 0.5-mL injection of Prevnar 13 into the right anterolateral thigh.
- Administer DTaP-containing vaccine and other permitted vaccines (to be administered into a limb other than the site of c7vPnC injection).
- Site staff will observe the subject for at least 30 minutes after vaccination for any acute reactions. Record any AEs on the CRF and on an SAE form as applicable. Record concomitant medications used to treat SAEs and NDCMCs.

- Issue the subject's legally acceptable representative a measuring device to measure injection site reactions and a digital thermometer and provide instructions on their use.
- Issue the subject's legally acceptable representative an e-diary (device or application). Provide instructions on use and completion of the e-diary. Ask the subject's legally acceptable representative to complete the e-diary from Day 1 to Day 7, with Day 1 being the day of vaccination.

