9.4. Safety Analysis

All safety analyses will be performed using the safety population.

Descriptive statistics for local reactions for the c7vPnC injection site in Groups 1 and 2 and the Supplemental Dose in Group 3, as well as the Prevnar 13 site in Group 3, and systemic events from Day 1 to Day 7 will be presented by severity and cumulatively across severity levels. Descriptive statistics will include proportions of subjects with the indicated endpoint and the associated Clopper-Pearson 95% CIs. Local reactions will be compiled for each dose for each group (Doses 1, 2, 3, and 4 and the Supplemental Dose) separately and compiled across all 4 doses of the same group.

AEs (including nonserious AEs, SAEs, and NDCMCs) will be compiled over 2 intervals: from Dose 1 to 1 month following Dose 3 and from Dose 4 to 1 month following Dose 4/Supplemental Dose. SAEs and NDCMCs will be summarized from Dose 1 until 6 months after Dose 4/Supplemental Dose. The descriptive statistics for AEs will be summarized as the number and percentage of subjects reporting at least 1 event of each preferred term with the associated Clopper-Pearson 95% CIs, arranged by system organ class.

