6.1.2. Systemic Events

6.1.2.1. Primary Analysis

Endpoints: Proportions of subjects reporting prompted systemic events (fever, decreased appetite, irritability, and drowsiness/increased sleep) within 7 days of each dose

- Analysis time points: Within 7 Days Dose 1; Within 7 Days Dose 2; Within 7 Days Dose 3; Within 7 Days Dose 4; Within 7 Days Supplemental Dose
- Analysis population: Dose 1 to Dose 3 safety population for Doses 1 to 3, Dose 4 safety population for Dose 4, Supplemental dose safety population for supplemental Dose
- Analysis methodology: Descriptive statistics
- Supporting objective: Primary Objective

Reporting results:

The percentage (%) and the numerator (n) and the denominator (N) used in the percentage calculation, and corresponding 95% Clopper-Pearson CI will be presented for each vaccine group at each time points.

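### Two of the six paired limits in the Protocol's fever-range table do not convert: 101.2°F is not 38.5°C, and 102.1°F is not 39.0°C

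*Protocol*

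**What the plan says.** Protocol section 7.1.2.2.2 (Fever) states: "Temperature will be measured and recorded to 1 decimal place and then grouped into ranges for the analysis". Table 4 in that section gives four ranges, each in both units:

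- Range 1: "100.4°F to 101.1°F (38.0°C to 38.4°C"
- Range 2: "101.2°F to 102.0°F (38.5°C to 38.9°C"
- Range 3: "102.1°F to 104.0°F (39.0°C to 40.0°C"
- Range 4: ">104.0°F (>40.0°C"

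Protocol section 9.4 states how they are used: "systemic events from Day 1 to Day 7 will be presented by severity and cumulatively across severity levels". Table 3 grades the other systemic events but not fever, so Table 4 is the only visible grouping for fever. SAP section 6.1.2.1 names the endpoint: "Proportions of subjects reporting prompted systemic events (fever, decreased appetite, irritability, and drowsiness/increased sleep) within 7 days of each dose". Its visible reporting text asks for percentages and Clopper-Pearson intervals, and mentions neither temperature ranges nor a unit.

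The visible text of both documents names no governing unit for the grouping and gives no conversion or rounding rule.

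**The concern.** A table that states the same cut-points in two units must put every reading in the same range whichever column is applied. At two boundaries Table 4 does not. The count in each middle range then depends on which column the programmer codes, and the visible plan does not say which that is.

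The labels are also at stake. If grouping is done in Fahrenheit and the output carries the printed Celsius labels, a row headed 39.0°C to 40.0°C would include infants whose highest reading was 102.1°F, which is 38.9°C. A reader comparing that row with another study's results from 39.0°C upward would be comparing slightly different things.

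**Working it through.** **Inputs.** The six paired limits of Table 4, and the one-decimal recording precision in Protocol section 7.1.2.2.2.

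**Formulas.** C = (F − 32) × 5/9 and F = C × 9/5 + 32, each rounded to one decimal (half up).

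**Step 1: convert the printed limits.**

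| Printed pair | °F to °C | °C to °F | Agrees at 1 decimal? |
|---|---|---|---|
| 100.4 / 38.0 | 38.00 | 100.40 | yes |
| 101.1 / 38.4 | 38.39 → 38.4 | 101.12 → 101.1 | yes |
| 101.2 / 38.5 | 38.44 → 38.4 | 101.30 | **no** |
| 102.0 / 38.9 | 38.89 → 38.9 | 102.02 → 102.0 | yes |
| 102.1 / 39.0 | 38.94 → 38.9 | 102.20 | **no** |
| 104.0 / 40.0 | 40.00 | 104.00 | yes |

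Four of the six pairs reproduce. The two that do not are the lower limits of ranges 2 and 3. In each, the Fahrenheit figure is 0.1°F below the Celsius figure printed beside it.

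**Step 2: find the readings that change range.** Every 0.1° reading from 98.0 to 107.9°F and from 36.5 to 42.4°C was placed in a range in its own unit and again after conversion.

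- Fahrenheit to Celsius: exactly two readings change. 101.2°F is in range 2, but as 38.4°C it is in range 1. 102.1°F is in range 3, but as 38.9°C it is in range 2.
- Celsius to Fahrenheit: none change.

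**Step 3: see whether another rounding rule rescues the table.**

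- Always rounding down keeps both mismatches and adds a third: 104.1°F (40.06 → 40.0°C) drops from range 4 to range 3.
- Always rounding up removes the two, but turns 100.3°F (37.94 → 38.0°C) into a fever. It also moves 38.4°C (101.12 → 101.2°F) and 38.9°C (102.02 → 102.1°F) up a range.

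None of the three rules makes the printed limits consistent.

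**Step 4: size.** From 100.4 to 104.0°F there are (104.0 − 100.4)/0.1 + 1 = 37 one-decimal readings. Two are affected: 2/37 = 5.4% of the possible values. One of them crosses the 39.0°C line: 1/37 = 2.7%.

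These are shares of the scale, not of infants. The summary counts subjects, and non-febrile subjects stay in the denominator. If a fraction f of an arm has fever, and the highest readings are spread evenly over the 37 values (an assumption), about f × 2.7% of the arm sits at each cut. With the planned 188 infants per arm, one infant changing range moves a proportion by 1/188 = 0.5 percentage points.

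**Step 5: check a corrected set.** With Fahrenheit limits 100.4–101.2, 101.3–102.1, 102.2–104.0 and >104.0, and the Celsius limits unchanged, no 0.1° reading changes range in either direction under half-up rounding.

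**The case against.** The strongest reply is that within a single unit there is no ambiguity. At one decimal the Fahrenheit ranges are contiguous, and so are the Celsius ranges. All sites are in the United States, and one e-diary contact value in section 7.1.2.2.2 is given in Fahrenheit only, which suggests Fahrenheit entry. The fields at site visits that allow either unit ("Measure and record the subject's rectal temperature (°F/°C") are prevaccination temperatures, not the diary readings behind the endpoint. Parts of the SAP that could define the fever summary are redacted, and section 5.3 breaks off mid-sentence, so a governing unit may be stated where it cannot be seen. The study is descriptive, so no test or decision turns on 0.1°F.

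Most of this stands, and it rules out several stronger readings that a reader might infer:

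- *That the table as a whole fails to convert.* Four of the six pairs and the top range are sound.
- *That the primary fever proportion is wrong.* The any-fever cut-off converts exactly.
- *That mixed-unit diary data will be grouped inconsistently.* Nothing in the documents shows that diary data will come in both units.
- *That the plan never names a unit.* Only the visible text can be said to be silent.
- *That some readings fall in no range.* This needs unrounded conversion, which no visible text plans.
- *That about 5% of fevers would be misplaced.* The 2/37 is a share of the scale, and only 1/37 concerns the 39.0°C cut.

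The reply does not remove the printed mismatch. Naming Fahrenheit would settle the grouping, but the Celsius labels on ranges 2 and 3 would still be wrong for readings at their lower limits.

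**Conclusion.** The fault is real and small. Two of Table 4's six paired limits are inconsistent by 0.1°F, and exactly two one-decimal Fahrenheit readings (101.2 and 102.1) change range with the unit. The effect is confined to the split between ranges 1 and 2 and between ranges 2 and 3 in a descriptive fever summary.

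The arithmetic rests only on the printed limits and half-up rounding to one decimal. The effect on infants depends on how highest temperatures are distributed, which the documents do not give. Under an even spread it is below 3% of an arm at either cut, and lower in proportion to the share without fever. It merits correction because the section says these ranges are used for analysis, but no conclusion of the study depends on it.

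**What to change.** Reconcile the two columns of Table 4. One option keeps the Celsius limits and prints the Fahrenheit ranges as 100.4–101.2, 101.3–102.1, 102.2–104.0 and >104.0; the check above shows that this set is consistent in both directions. Then state, in Table 4 or in the SAP's systemic-event section, the single unit used for grouping and the rounding applied if a reading is converted. If the sponsor prefers to keep the Fahrenheit limits, the Celsius labels should be dropped or marked as approximate in the outputs.

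This concerns analysis ranges only. It leaves the fever definition and the contact instructions to parents untouched. The cost is a table correction and one sentence, with no change to data collection and a negligible shift in range counts.

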7.2. Immunogenicity

Blood samples (approximately 5 mL/visit) for immunogenicity assessments will be collected from all subjects 1 month after Dose 3, prior to Dose 4, and 1 month after Dose 4, In Group 2, blood will also be collected prior to Dose 3. Sample collection, processing, storage, and shipping information can be found in the SRM or equivalent manual.

Concentrations of anticapsular polysaccharide IgG antibodies for the 7 vaccine serotypes will be determined on sera collected at each blood draw in all subjects. The serotype-specific IgG concentrations will be measured by Pfizer's Luminex-based assay.

For samples being collected and shipped, detailed collection, processing, storage, and shipment instructions and contact information will be provided to the investigator site prior to initiation of the study. Serum samples should be processed and stored as indicated in the SRM or equivalent document.

Immunogenicity assays will be performed at the Pfizer Vaccine Research & Development laboratory located at [name] and/or at an external laboratory designated by Pfizer.

7.3. Biological Samples

Blood samples will be used only for scientific research. Each sample will be labeled with a code so that the laboratory personnel testing the samples will not know the subject's identity.

Samples that remain after performing assays outlined in the protocol may be stored by Pfizer. Unless a time limitation is required by local regulations or ethical requirements, the samples will be stored for up to 15 years after the end of the study and then destroyed.

No testing of the subject's genetic material will be performed.

The subject's legally acceptable representative may request that his or her child's samples, if still identifiable, be destroyed at any time; however, any data already collected from those samples will still be used for this research. The biological samples may be shared with other researchers as long as confidentiality is maintained and no testing of the subject's genetic material is performed.

8. ADVERSE EVENT REPORTING

8.1. Requirements

The table below summarizes the requirements for recording safety events on the CRF and for reporting safety events on the Clinical Trial (CT) SAE Report Form to Pfizer Safety. These requirements are delineated for 3 types of events: (1) SAEs; (2) nonserious AEs; and (3) exposure to the investigational product under study during pregnancy or breastfeeding, and occupational exposure.

Safety Event	Recorded on the CRF	Reported on the CT SAE Report Form to Pfizer	
		Safety Within 24 Hours of	
		Awareness	
SAE	All	All	
Nonserious AE ^a	All	None	
Exposure to the	All (regardless of whether	Exposure during pregnancy,	
investigational product	associated with an AE), except	exposure via breastfeeding,	
under study during	occupational exposure	occupational exposure	
pregnancy or breastfeeding,		(regardless of whether	
and occupational exposure		associated with an AE)	

a. Nonserious AEs will be recorded from the time the subject provides informed consent through 1 month after Dose 3 and from Dose 4 to 1 month after Dose 4/Supplemental Dose. Newly diagnosed chronic medical conditions (can be nonserious) and SAEs will be reported from the time the subject provides informed consent through 6 months after Dose 4/Supplemental Dose.

All observed or volunteered events regardless of vaccine group or suspected causal relationship to the investigational product(s) will be reported as described in the following paragraphs.

Events listed in the table above that require reporting to Pfizer Safety on the CT SAE Report Form within 24 hours of awareness of the event by the investigator are to be reported regardless of whether the event is determined by the investigator to be related to an investigational product under study. In particular, if the SAE is fatal or life-threatening, notification to Pfizer Safety must be made immediately, irrespective of the extent of available event information. This time frame also applies to additional new (follow-up) information on previously forwarded reports. In the rare situation that the investigator does not become immediately aware of the occurrence of an event, the investigator must report the event within 24 hours after learning of it and document the time of his/her first awareness of the event.

For each event, the investigator must pursue and obtain adequate information both to determine the outcome and to assess whether it meets the criteria for classification as an SAE

Final Protocol Amendment 1, 18 Feb 2020

(see the SAE section below). In addition, the investigator may be requested by Pfizer Safety to obtain specific follow-up information in an expedited fashion. This information is more detailed than that recorded on the CRF. In general, this will include a description of the event in sufficient detail to allow for a complete medical assessment of the case and independent determination of possible causality. Any information relevant to the event, such as concomitant medications and illnesses, must be provided. In the case of a subject death, a summary of available autopsy findings must be submitted as soon as possible to Pfizer Safety. Any pertinent additional information must be reported on the CT SAE Report Form; additional source documents (eg, medical records, CRF, laboratory data) are to be sent to Pfizer Safety **ONLY** upon request.

As part of ongoing safety reviews conducted by the sponsor, any nonserious AE that is determined by the sponsor to be serious will be reported by the sponsor as an SAE. To assist in the determination of case seriousness, further information may be requested from the investigator to provide clarity and understanding of the event in the context of the clinical study.

8.1.1. Additional Details on Recording Adverse Events on the CRF

All events detailed in the table above will be recorded on the AE page(s) of the CRF. It should be noted that the CT SAE Report Form for reporting of SAE information is not the same as the AE page of the CRF. When the same data are collected, the forms must be completed in a consistent manner. AEs should be recorded using concise medical terminology and the same AE term should be used on both the CRF and the CT SAE Report Form for reporting of SAE information.

8.1.2. Eliciting Adverse Event Information

The investigator is to record on the CRF all directly observed AEs and all AEs spontaneously reported by the study subject's legally acceptable representative. In addition, each study subject's legally acceptable representative will be questioned about the occurrence of AEs in a nonleading manner.

8.1.3. Withdrawal From the Study Due to Adverse Events (see also the Subject Withdrawal Section)

Withdrawal due to AEs should be distinguished from withdrawal due to other causes, according to the definition of AE noted below, and recorded on the CRF.

When a subject withdraws from the study because of an SAE, the SAE must be recorded on the CRF and reported, as appropriate, on the CT SAE Report Form, in accordance with the Requirements section above.

8.1.4. Time Period for Collecting AE/SAE/NDCMC Information

The time period for actively eliciting and collecting AEs, SAEs, and NDCMCs ("active collection period") for each subject begins from the time the subject's legally acceptable representative provides informed consent, which is obtained before the subject's participation in the study (ie, before undergoing any study-related procedure and/or receiving

investigational product). AEs will be collected through 1 month after Dose 3 and from Dose 4 through 1 month after Dose 4 or 1 month after the Supplemental Dose in Group 3. NDCMCs and SAEs will be collected from signing of informed consent through 6 months after Dose 4 or the Supplemental Dose. An NDCMC is defined as a disease or medical condition, not previously identified, that is expected to be persistent or is otherwise long-lasting in its effects.

For subjects who are screen failures, the active collection period ends when screen failure status is determined.

